All patients who receive a dose of pembrolizumab and trametinib will be analyzed for safety and efficacy. Subjects who discontinue from study participation prior to receiving the combination of trametinib and pembrolizumab will be replaced. Subjects in dose escalation who discontinue from study and are not evaluable for dose limiting toxicities will be replaced. Patients removed from study for unacceptable treatment related adverse event(s) will be followed until resolution or stabilization of all treatment related AEs to grade 2 or lower. However, they will not be replaced.

A group of 12 patients will be enrolled in each of the 2 expansion cohorts at the MTD. Patients will enroll into the next subsequent cohort upon completion of the previous cohort (Arm A then Arm B). A sequencing scheme will be considered as promising if at least 5 of 12 patients were to achieve a complete or partial response per RECIST 1.1. The decision rule is associated with 80% exact power with an exact alpha of 0.16 if the underlying response rate associated with a sequencing scheme were truly at least 50% compared to current expectation of 25% ORR with single agent pembrolizumab. A median PFS of 8 months in 12 patients per cohort will provide 81 power to detect a difference compared to historical PFS of about 4 months with single agent pembrolizumab with an alpha of 0.1 based on accrual time of 24 months and follow up of 12 months. A sequencing scheme will be recommended for further development based on a combination of promising efficacy (response rate, PFS) and favorable changes in the tumor immune microenvironment at rebiopsy, provided the safety and tolerability profiles are acceptable.

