All molecular and immune correlates will be assessed in exploratory analyses. Due to the limited sample size and exploratory framework, any such analysis will be stated carefully as hypothesisgenerating with the reported p-values not adjusted for multiple comparisons. Standard descriptive and graphical methods will be used to summarize the baseline levels and post-treatment changes for comparison of the three MEKi and pembrolizumab sequencing schemes, which will allow us to examine whether observed patterns are consistent with hypothesized mechanisms. The quantitative immune studies will be compared using a t-test to further inform the decision. Multiplicity of testing will not be considered since this considered an exploratory analysis. Association with response rate will be summarized descriptively by presenting the mean, SD, and other characteristics of molecular and immune measures, stratified by response status. Associations of molecular and immune measures with PFS will be summarized descriptively by stratified Kaplan-Meier curves and, if numbers permit, by proportional hazards models with molecular and immune responses as predictors. If the MEKi and pembrolizumab combination were not found to have sufficient activity, the molecular and immune patterns may

help explain the lack of activity. If sufficient activity were observed, then the correlates will be compared between patients who experience an objective response and those who did not. Results of these correlative studies including biopsies at pre-treatment and week 1 on treatment will be analyzed in conjunction with the Battle-Immunotherapy trial (with its later biopsy correlative timepoints) to inform the optimal dosing and sequencing of pembrolizumab with trametinib.

Decisions for whether to pursue one of these strategies in a larger trial will incorporate ORR, toxicity and immune correlative endpoints in collaboration with the company sponsors and SU2C Dream Team. The primary considerations will be ORR and toxicity, with immune and genomic correlative studies used as supplementary criteria.

If only one arm meets safety criteria and preliminary efficacy criteria (ORR \geq 50% or a median PFS \geq 8 months), then that treatment will be considered for future study. Immune and genomic correlative studies will be examined for the potential to inform future study design for that arm.

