If both arms A and B meet the safety criteria and preliminary efficacy criteria and give comparable response rates and toxicities, we will carry out two additional sets of analyses to inform the decision process of which treatment to pursue for further study. First, we will use regression models to assess whether one arm might have superior performance after accounting for key patient differences (PD-L1 status, KRAS amino acid substitution (G12C vs. non-G12C), smoking status). We will assess whether one arm has superior ORR, using logistic regression analysis to control for clinical covariates, and whether one arm has superior PFS, using proportional hazards models to control for clinical covariates. Second we Second, we will examine biomarkers that might shed light on the impact of the treatments. We will compare exploratory immune correlates (enhanced tumor immune microenvironment). The final decision will be based on best clinical judgment of all investigators.

We expect that the distribution of PD-L1 expression in Arm A and Arm B to be comparable. Based on the current indication for first line pembrolizumab in PD-L1 high (>50%) NSCLC, the majority of patients accrued into this second line trial will likely contain tumors with lower PD-L1 expression. At completion of Arm A we will review baseline characteristics and current clinical practice at that time to assess whether it is anticipated there would be a shift in biomarker distribution in Arm B.

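### The plan gives two efficacy thresholds for the same 12-patient arms (at least 5/12 responses; ORR at least 50% or median PFS at least 8 months), and its stated error rates fit only the first

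*Combined protocol and SAP*

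**What the plan says.** Section 8.0 sets the response rule in its paragraph on the expansion cohorts: "A sequencing scheme will be considered as promising if at least 5 of 12 patients were to achieve a complete or partial response". The next sentence gives its error rates: "The decision rule is associated with 80% exact power with an exact alpha of 0.16". The alternative is a true response rate of 50% and the comparator is 25% for single-agent pembrolizumab.

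The same paragraph gives a PFS calculation: "A median PFS of 8 months in 12 patients per cohort will provide 81 power to detect a difference". The comparison is with a historical median of about 4 months, at alpha 0.1, with 24 months of accrual and 12 months of follow-up. The paragraph then says how the two endpoints are used: "A sequencing scheme will be recommended for further development based on a combination of promising efficacy (response rate, PFS"), together with immune changes at rebiopsy and acceptable safety.

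Later in Section 8.0 a different standard appears. The sentence opening "If only one arm meets safety criteria and preliminary efficacy criteria" defines those criteria in brackets as ORR of at least 50% or median PFS of at least 8 months. The following paragraph reuses the label to trigger the between-arm analyses: "If both arms A and B meet the safety criteria and preliminary efficacy criteria and give comparable response rates and toxicities". Section 2.1 names the same pair, joined by 'or', as enough to take an arm forward if safety is acceptable.

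Just before the bracketed criteria, Section 8.0 says: "Decisions for whether to pursue one of these strategies in a larger trial will incorporate ORR, toxicity and immune correlative endpoints". PFS is not named there.

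**The concern.** Five responses of 12 is 41.7%, which meets the first rule and fails a 50% cut-off. A reader who takes the published 80% power and 0.16 alpha to describe the criteria used later in Section 8.0 would be misled, because those figures belong to another threshold. The same holds for PFS: power for a test against 4 months does not describe whether an observed median reaches 8 months.

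The way the endpoints are joined is also open. One sentence weighs response rate and PFS in combination. Two other places let either suffice. A further sentence leaves PFS out of the decision, and shortly afterwards PFS alone can qualify an arm.

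At stake is whether an arm qualifies for further study. If that is unsettled when the data arrive, an arm with 5 responses and a median PFS below 8 months can be described either way after the fact.

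**Working it through.** **Inputs from Section 8.0.** 12 patients per expansion cohort; response rates 25% (null) and 50% (target); median PFS 4 months (null) and 8 months (target); PFS alpha 0.1; accrual 24 months; follow-up 12 months.

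**1. The plan's ORR figures.** With X ~ Binomial(12, p):

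| Rule | Alpha, p = 0.25 | Power, p = 0.50 |
|---|---|---|
| X ≥ 5 (41.7%) | 0.158 | 0.806 |
| X ≥ 6 (50%) | 0.054 | 0.613 |

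The first row reproduces the stated 0.16 and 80%. The second row is what an observed ORR of at least 50% means with 12 patients. The rules disagree at X = 5, which has probability 0.806 − 0.613 = 0.193 at a true 50% and 0.158 − 0.054 = 0.103 (rounded inputs give 0.104) at a true 25%.

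**2. The plan's PFS power.** Assume exponential PFS and uniform accrual. With λ = ln 2/8 = 0.0866, the chance of an observed event is 1 − (e^(−12λ) − e^(−36λ))/(24λ) = 1 − (0.3536 − 0.0442)/2.079 = 0.851. Expected events are 12 × 0.851 = 10.2. Power for a hazard ratio of 0.5 is Φ(√10.2 × ln 2 − z):

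- one-sided 0.1 (z = 1.282): 0.825
- two-sided 0.1 (z = 1.645): 0.716

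The stated 81 is close to the one-sided figure. The plan does not state sidedness.

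**3. Observed median of at least 8 months.** Take the Kaplan-Meier median as the sixth of 12 event times, with no censoring before month 8. The criterion is then met when at most 5 of 12 patients have an event by month 8. The event probability by month 8 is 0.50 at a true median of 8 and 0.75 at a true median of 4.

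- True median 8: P(at most 5 events) = 0.387
- True median 4: P(at most 5 events) = 0.014

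Neither figure appears in the plan, and 0.387 is well below the stated 81.

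**4. Joining the two endpoints.** If response and PFS are independent:

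- 'Or' at the target: 1 − (1 − 0.613)(1 − 0.387) = 0.763
- 'Or' at the null: 1 − (1 − 0.054)(1 − 0.014) = 0.068 (unrounded inputs)
- 'And' at the target: 0.613 × 0.387 = 0.237
- 'And' at the null: 0.054 × 0.014 = 0.001

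The plan gives no correlation and no median convention. A simulation with exponential PFS, a Gaussian copula with correlation 0, 0.5 or 0.8, and 200,000 trials per setting gives these ranges. They cover the three correlations and two median conventions (sixth event, or midpoint of the sixth and seventh).

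| | Target (50%, 8 months) | Null (25%, 4 months) |
|---|---|---|
| ORR ≥ 50% or median ≥ 8 | 67–81% | 6–8% |
| ORR ≥ 50% and median ≥ 8 | 24–42% | 0.1–1.1% |
| Exactly 5/12 and median < 8 | 10–15% | about 10% |

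**5. Sensitivity to the scan schedule.** Section 6.0 sets imaging every 9 weeks. If 4 and 8 months are latent medians and progression is dated at the next 63-day scan, the 'or' rule reaches up to about 88% at the target and 13% at the null. These are too high if the historical 4 months is already scan-based.

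**The case against.** The strongest reply is that the texts need not conflict. Section 8.0 uses one term, promising, for 5 of 12, and another, recommendation or future study, for the stricter pair, so a two-tier scheme is a possible reading. The 50% and 8 months also equal the design alternatives, so they may have been meant as target true values. Section 2.1 words the pair as an anticipated sufficient condition, and nothing says an arm that misses it is dropped. Both readings are open, but the plan states neither. Section 8.0 words the pair as criteria an arm meets, and only observed results can be met.

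The consequence is also limited, and that stands. Section 3.2 makes efficacy a secondary, preliminary objective. An arm that meets the criteria is only considered for future study. When both arms qualify, the investigators' clinical judgment decides. The 'or' rule's false-go rate stayed below the stated 0.16 in every setting tried, and its power fell on both sides of 80%.

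Two technical points are fair but do not change the direction. Early withdrawal or new therapy could censor PFS before month 8, which step 3 ignores. The denominator might not be 12: Section 8.0 elsewhere cites 16 patients at the MTD, and with 16 patients a 50% cut-off means at least 8 responses, with alpha 0.027 and power 0.598.

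**Conclusion.** The concern holds. The plan names at least 5 of 12 responses as its decision rule and gives error rates for that rule only, then judges the same arms on ORR of at least 50% or median PFS of at least 8 months, without linking the two.

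The ORR results need only the documents' inputs: moving from 5 to 6 responses takes power from 0.806 to 0.613 and alpha from 0.158 to 0.054. The PFS and joint figures rest on exponential PFS, no early censoring, a median convention and a response-PFS correlation that the plan does not give, so they are ranges. Whether the endpoints are joined by 'or' or by 'and' matters more than the one-response difference: power at the target is 67–81% against 24–42% in continuous time.

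This should be fixed. It does not bear on the primary safety objective, and it is not a claim that the error rate is inflated.

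**What to change.** Use one efficacy rule in Section 2.1 and throughout Section 8.0. Two ways are open:

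- (a) Make at least 5 of 12 responses and the 0.1-level PFS test against 4 months, with its sidedness stated, the efficacy criteria in place of 50% and 8 months.
- (b) Keep 50% and 8 months as observed cut-offs, restate the ORR figures as power 61% and alpha 0.054, and replace the PFS power with a figure for the observed-median cut-off, naming the median convention.

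In either case say whether ORR and PFS are joined by 'or' or by 'and', and report the combined operating characteristics with their assumptions. If 50% and 8 months are target true values, say that they are not cut-offs. If two tiers are intended, say so and give figures for each.

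The cost is some wording and a short calculation, with no extra patients. The drawback is that the stated figures may look less favourable, for example an ORR power of 61% under (b).

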2.0 TRIAL DESIGN

2.1 Trial Design

This is a trial for patients with advanced or metastatic non-small cell lung cancer patients with KRAS mutations who have progressed on prior platinum-based frontline therapy. After the initial dose escalation with two different sequencing schemes (lead in trametinib and lead in pembrolizumab), in the expansion cohorts patients will be allocated to one of these two different arms: a) lead in trametinib followed by the intermittent trametinib/pembrolizumab and b) lead in pembrolizumab followed by intermittent pembrolizumab and trametinib to further define toxicities at the MTD, to determine the RP2D, to assess initial estimates of efficacy and to examine in the tumor and immune microenvironment changes in PD-L1 expression and T-cell subsets) across these two different sequencing schemes. Safety findings and preliminary efficacy will be employed as primary criteria for whether one or both treatment sequences may warrant further study. Exploratory immune correlates will be examined as secondary criteria to inform further development of this approach in future studies. The treatment arm that provides the better RR, PFS, safety profile and enhanced tumor immune microenvironment at rebiopsy will be recommended for further development. It is anticipated that $ORR \ge 50\%$ or a median PFS ≥ 8 months would be sufficient to recommend further development, provided safety and tolerability are acceptable. Patients will be treated until progression per RECIST 1.1 guidelines or intolerable toxicity.

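### The stated alphas and powers are each for one endpoint in one arm and do not describe the ORR-or-PFS rule by which an arm qualifies

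*Combined protocol and SAP*

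**What the plan says.** Section 8.0 sets the size: "A group of 12 patients will be enrolled in each of the 2 expansion cohorts at the MTD". A sequence is promising if "at least 5 of 12 patients were to achieve a complete or partial response per RECIST 1.1". The operating characteristics follow: "The decision rule is associated with 80% exact power with an exact alpha of 0.16 if the underlying response rate" is "truly at least 50% compared to current expectation of 25% ORR with single agent pembrolizumab". PFS has its own calculation, a median of 8 months in 12 patients with 81% power against "historical PFS of about 4 months with single agent pembrolizumab with an alpha of 0.1". The PFS test and the sidedness of its alpha are not named.

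The rule for moving forward is worded in three ways:

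- Section 2.1 anticipates that an ORR of at least 50% "or a median PFS ≥ 8 months would be sufficient to recommend further development", subject to acceptable safety. Section 8.0 repeats the same two marks, joined by *or*, as the preliminary efficacy criteria.
- Section 8.0, directly after the power figures: "A sequencing scheme will be recommended for further development based on a combination of promising efficacy (response rate, PFS) and favorable changes" in the immune microenvironment, again subject to safety.
- Section 8.0, on whether to pursue a larger trial: "The primary considerations will be ORR and toxicity, with immune and genomic correlative studies used as supplementary criteria". PFS is not mentioned in that sentence.

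The only statements on multiplicity sit in the paragraph on molecular and immune correlates. The final choice between two qualifying arms is left to the investigators' clinical judgment.

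**The concern.** The figures that justify 12 patients per arm belong to two separate tests. The rule by which an arm qualifies uses a different response mark (6 of 12, not 5 of 12), apparently an observed median in place of a PFS test, and a choice of endpoint in each of two arms. A reader who takes 0.16 and 80% as the properties of the go decision is therefore misinformed. Whether the true error is higher or lower depends on which sentence is followed.

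The role of PFS matters most when the endpoints disagree. PFS is enough alone under the *or* wording, is listed as part of the efficacy evidence in the second wording, and has no place in the third. In an open-label trial with 12 patients per arm, that leaves room to settle the rule after the results are known.

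**Working it through.** **Inputs from Section 8.0.** n = 12 per arm; two arms with different patients, treated as independent; response rate 25% null and 50% alternative; median PFS 4 months null and 8 months alternative; PFS alpha 0.1; accrual 24 months, follow-up 12 months. **Assumptions:** exponential PFS, uniform accrual, and a response-PFS correlation that the documents do not give, so ranges are shown.

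**1. The plan's own figures.** ORR: P(X ≥ 5 | 12, 0.25) = 0.158 and P(X ≥ 5 | 12, 0.50) = 0.806. Both reproduce.

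PFS: with median 8 months, λ = ln 2 / 8 and expected events are 12 × [1 − (e^(−12λ) − e^(−36λ)) / (24λ)] = 10.2. A log-hazard test at one-sided 0.1 has power Φ(0.693 × √10.2 − 1.282) = 0.825. A one-sample log-rank test at two-sided 0.1 gives Φ(√10.2 − 1.645 × √2) = 0.808. Both are close to 81%, so the sidedness cannot be settled from the power figure.

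**2. ORR alone in two arms.** 1 − (1 − 0.158)² = 0.29. This needs no correlation and no PFS assumption.

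**3. The two stated tests joined by *or*.** Per arm, the rate under any dependence lies between max(0.16, 0.10) = 0.16 and 0.16 + 0.10 = 0.26. For at least one arm: 1 − 0.84² = 0.29 to 1 − 0.74² = 0.45. Under independence: 0.16 + 0.10 − 0.016 = 0.244 per arm and 1 − 0.756² = 0.43. If the 0.1 is two-sided, with 0.05 in the favourable tail, independence gives 0.16 + 0.05 − 0.008 = 0.202 and 1 − 0.798² = 0.36.

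**4. The printed marks (at least 6 of 12, or observed median at least 8 months).** P(X ≥ 6 | 12, 0.25) = 0.054 and P(X ≥ 6 | 12, 0.50) = 0.613. With 12 months' minimum follow-up, nobody is administratively censored before month 8. The Kaplan-Meier median then reaches 8 months when at most 5 of 12 have progressed or died by then:

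- true median 4: the chance of an event by month 8 is 1 − 0.5² = 0.75, and P(≤ 5 of 12) = 0.014;
- true median 8: the chance is 0.5, and P(≤ 5 of 12) = 0.387.

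Under independence the false-go rate is 1 − 0.946 × 0.986 = 0.068 per arm and 1 − 0.932² = 0.13 for either arm; power is 1 − 0.387 × 0.613 = 0.76. Simulation (200,000 trials, Gaussian copula between response and PFS) at correlation 0.8 gives 0.061, 0.12 and 0.67. If the median is instead taken as the mean of the 6th and 7th ordered times, the same simulation over correlations 0 to 0.8 gives 0.07 to 0.08 per arm, 0.13 to 0.15 for either arm, and power 0.81 to 0.70.

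| Efficacy rule | False go, per arm | False go, either arm | Power, per arm |
|---|---|---|---|
| ORR ≥ 5/12 alone | 0.158 | 0.29 | 0.806 |
| ORR ≥ 6/12 alone | 0.054 | 1 − 0.946² = 0.11 | 0.613 |
| ≥ 5/12 or PFS test at 0.1 | 0.16–0.26 | 0.29–0.45 | 0.92 at test correlation 0.5 |
| ≥ 6/12 or median ≥ 8 months | 0.06–0.07 | 0.12–0.13 | 0.67–0.76 |

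**5. How often the wording decides the outcome.** Exactly 5 of 12 responses passes one ORR mark and fails the other. At a true rate of 50% this has probability 0.806 − 0.613 = 0.19. Using the stated tests, an active arm passes one endpoint and fails the other with probability 0.806 × 0.19 + 0.194 × 0.81 = 0.31 under independence, and about 0.22 at correlation 0.5.

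**The case against.** This is a phase Ib trial whose primary objective is safety; efficacy is secondary and preliminary. Each alpha is correct for its own test and is never presented as a joint rate. Each arm is judged against historical figures and both may go forward, so familywise control across arms is not expected. Safety, immune findings and clinical judgment also stand between a positive result and a recommendation. All of this stands. It removes any demand for formal error control and limits the figures above to the efficacy criterion.

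Three stronger readings are tempting, and the documents do not support them:

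- *The stated alphas understate the false-go risk, at about 0.38 across the trial.* That figure joins 5 of 12 with the PFS test at 0.1, and needs an assumed test-level correlation of 0.5. The printed *or* uses stricter marks, and there the risk is below 0.16 even across both arms.
- *There is no hierarchy.* Section 8.0 does put ORR and toxicity first. The difficulty is that this gives PFS no place and conflicts with the *or*.
- *The combination sentence makes a split result a no-go.* Its *and* joins efficacy to immune changes; the bracket lists efficacy measures without requiring both.

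What the objection leaves untouched is that no operating characteristics are given for the *or* rule, and the ones printed beside the sample size belong to other rules.

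**Conclusion.** The point holds as a mismatch between the stated operating characteristics and the go rule. The direction of the error depends on the reading. Joining the two stated tests makes false positives more likely than 0.16 or 0.1 suggest: 0.24 per arm and 0.43 for either arm under independence. Applying the printed marks makes them less likely than 0.16, at the price of power: 61% on ORR alone, and about 0.67 to 0.76 for the *or* rule against the stated 80%. Two cautions apply to that last range. It rests on exponential PFS and an assumed correlation of 0 to 0.8, and under the other median convention power reaches 0.81 at zero correlation. The 5-of-12 ORR results are exact and need no such assumption. The plan should be corrected, but the documents do not establish that its go decision is lenient.

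**What to change.** In Sections 2.1 and 8.0, state one efficacy go rule with the same thresholds throughout. Say whether PFS can qualify an arm alone, is required together with ORR, or is supportive. Report that rule's per-arm false-positive rate and power, with the either-arm rate beside it; if 5 of 12 on ORR alone is the rule, these are 0.158, 0.806 and 0.29. If PFS can qualify an arm, add the assumed response-PFS correlation with a range. Name the PFS test or the convention for the observed median, and say whether the alpha of 0.1 is one- or two-sided.

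Making ORR the only trigger is one option and agrees with the sentence on primary considerations, but it is not required. Its price is that an arm succeeding on PFS alone would no longer qualify automatically.

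The change is to wording and needs no extra patients. The cost is that either the stated error rate or the stated power will look less favourable than it does now.

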From the time of treatment allocation/randomization through 30 days following cessation of treatment, all adverse events must be reported by the investigator. Such events will be recorded at each examination on the Adverse Event case report forms/worksheets. The reporting timeframe for adverse events meeting any serious criteria is described in section 7.2.3.1. The investigator will make every attempt to follow all subjects with non-serious adverse events for outcome.

7.2.1 Definition of an Overdose for this Protocol and Reporting of Overdose to the Sponsor Investigator and to Merck

For purposes of this trial, an overdose of pembrolizumab will be defined as any dose of 1,000 mg or greater (≥5 times the indicated dose). No specific information is available on the treatment of overdose of pembrolizumab. Appropriate supportive treatment should be provided if clinically indicated. In the event of overdose, the subject should be observed closely for signs of toxicity. Appropriate supportive treatment should be provided if clinically indicated.

If an adverse event(s) is associated with ("results from") the overdose of a Merck product, the adverse event(s) is reported as a serious adverse event, even if no other seriousness criteria are met.

If a dose of Merck's product meeting the protocol definition of overdose is taken without any associated clinical symptoms or abnormal laboratory results, the overdose is reported as a non-serious Event of Clinical Interest (ECI), using the terminology "accidental or intentional overdose without adverse effect."

All reports of overdose with and without an adverse event must be reported within 24 hours to the Sponsor Investigator and within 2 working days hours to Merck Global Safety. (Attn: Worldwide Product Safety; [contact])

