8.0 STATISTICAL ANALYSIS PLAN

The initial dose escalation will follow a standard 3+3 design, starting at dose level 1. The decision to escalate to the next dose level will be determined by the rate of dose-limiting toxicity (DLT) observed during Cycle 2, with a cycle length defined as 3 weeks. Up to 3 patients will be initially enrolled in a dose cohort, starting at dose level 1. If 1 of 3 patients were to experience DLT, 3 additional patients will be enrolled at same dose level. If 0 of 3 patients or 1 of 6 patients enrolled at a dose level were to experience DLT, enrollment to next dose level will be opened. If >1 of 3 patients or >1 of 6 patients enrolled at a dose level were to experience DLT, the maximum tolerated dose (MTD) will have been exceeded. Adverse events will be collected and described for the expansion cohorts. Enrollment to dose level 1 will be expanded to 6 patients if applicable, or enrollment to dose level -1 will be opened if dose level 1 were to exceed the MTD. The highest dose level at which 0 of 3 patients or 1 of 6 patients experience DLT will be declared the MTD. A minimum of 6 patients and maximum of 18 patients will be enrolled for each cohort (Arm A: Lead in Trametinib and Arm B: Lead in Pembrolizumab) in this dose escalation portion of the study.

Enrollment into Cohorts A and B are pre-planned in regards to sequence and timing. Arm A (lead in trametinib) will open 1st to dose escalation and will accrue 3 patients. Once 3 patients are accrued for Arm A, Arm B will open and accrue 3 patients. This is to ensure cohorts remain open for accrual given the 6-week DLT period; these cohorts will alternate in opening in this fashion until the MTD is achieved for both Arm A and Arm B. Once the MTD is achieved for both Arms A and B, Arm A will open to dose expansion at the MTD and complete accrual, followed by Arm B. If one Arm is delayed in opening additional dose levels due to toxicity, the alternate cohort may open at additional dose levels if approved by the Primary Investigator in consultation with Novartis and Merck.

The recommended dose expansion and recommended phase II dose (RP2D) will be determined by the overall assessment of the MTD and toxicities observed in the study.

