Assays will be performed at the SU2C Lung Cancer Dream Team Immune Monitoring Core, Yale University, The Broad Institute, UCSF and at UC Davis Comprehensive Cancer Center as part of the SU2C Dream Team Lung Cancer Collaboration. Next generation sequencing by the Broad Institute will perform whole exome DNA/RNA sequencing to confirm KRAS amino acid substitution and examine mutational load and other co-mutations of interest and well as changes in RNA expression of relevant gene in the tumor immune microenvironment. A subset analysis will explore clinical outcome by KRAS amino acid substitution (G12C vs. non-G12C). The immune correlative studies performed in baseline and repeat biopsy specimens include: (in order of priority) 1) IHC and IF to determine PD-L1 expression, MEK target inhibition 2) additional immunophenotyping, and functional assessment of tumor infiltrating immune cells 3) Luminex evaluation of local tumor cytokine / chemokine signatures. In blood, FACS for quantification, immunophenotyping, and functional assessment of PBMCs will also be performed.

Adverse events will be summarized descriptively by type and by severity, with number and relative frequency calculated for all non-zero occurrences. With 16 patients treated at the MTD for either regimen, we will have an at least an 81% chance of seeing one or more cases of any adverse event that occurs in 10% or more patients.

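### Crude adverse-event percentages are the only planned safety summary, so a difference in PFS between the arms can pass for a difference in toxicity when the sequences are compared

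*Combined protocol and SAP*

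**What the plan says.** The safety analysis in Section 8.0 is one sentence: "Adverse events will be summarized descriptively by type and by severity, with number and relative frequency calculated for all non-zero occurrences". The same paragraph adds a detection statement: "With 16 patients treated at the MTD for either regimen", the plan claims "at least an 81% chance of seeing one or more cases of any adverse event that occurs in 10% or more patients".

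Three other provisions matter.

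- **Collection window.** Section 7.2 requires that, from allocation "through 30 days following cessation of treatment, all adverse events must be reported by the investigator". Section 2.1 continues treatment to RECIST 1.1 progression or intolerable toxicity, so the length of the window differs between patients.
- **Use in the decision.** Section 8.0 states: "The primary considerations will be ORR and toxicity, with immune and genomic correlative studies used as supplementary criteria". If both arms meet the safety and efficacy criteria and their response rates and toxicities are judged similar, further analyses follow. Those adjust ORR (logistic regression) and PFS (proportional hazards) for covariates; none concerns adverse events. Section 2.1 also speaks of recommending the arm with the better response rate, PFS and safety profile.
- **Accrual order.** In the expansion phase, "Arm A will open to dose expansion at the MTD and complete accrual, followed by Arm B".

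No section gives a fixed-window comparison, an exposure-adjusted rate, a time-to-first-event analysis or a safety data cut-off for the expansion cohorts. The only fixed toxicity window is the DLT period in Section 5.4, which serves dose escalation.

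**The concern.** A crude percentage answers whether a patient ever had the event while being observed. Here patients are observed for as long as they stay on treatment plus 30 days, and that time is largely set by progression. Two sequences with the same toxicity per month on drug would then give different percentages if one controlled disease for longer.

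The stake is the choice of sequence. With toxicity ranked alongside ORR, part of any gap in the safety table could be a by-product of longer disease control, and the table as planned would not let a reader separate the two.

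**Working it through.** **1. The plan's own figure.** With 16 patients and a true rate of 10%, the chance of at least one case is 1 − 0.9^16 = 0.815, which matches the stated 81%. The calculation gives each patient one fixed 10% risk; time at risk does not enter.

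**2. Inputs for the check.**

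- Medians of 8 and 4 months: Section 8.0 (PFS target, and historical PFS with single-agent pembrolizumab). Medians of 10 and 12 months are illustrative.
- First-event hazard h = 0.05 per month, constant and equal in both arms: assumed.
- Follow-up F = 15.4 months: assumed.
- Exponential time on treatment with rate l = ln 2 / median. The 30-day tail is left out here and added in step 4.

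**3. Crude percentage.** P = h/(h + l) × (1 − exp(−(h + l)F)).

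| Median (months) | l | h/(h + l) | 1 − exp(−(h + l)F) | P | Patients of 12 |
|---|---|---|---|---|---|
| 4 | 0.1733 | 0.2239 | 0.968 | 0.217 | 2.6 |
| 8 | 0.0866 | 0.3659 | 0.878 | 0.321 | 3.9 |
| 10 | 0.0693 | 0.4191 | 0.841 | 0.352 | 4.2 |
| 12 | 0.0578 | 0.4640 | 0.810 | 0.376 | 4.5 |

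The 8 vs 4 month contrast gives a gap of about 10 points (32% vs 22%) with no true difference in hazard. If both arms reach the 8-month PFS criterion, the gap is 3 to 5 points (32% vs 35% to 38%), or 0.4 to 0.7 of a patient in 12.

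**4. Sensitivity to the assumptions.** A simulation added the 30-day tail and assumed potential follow-up spread evenly over 12 to 36 months. At medians of 4 vs 8 months and equal constant hazards, 20% became 30%, and 30% became 43%. With all risk in the first 6 weeks the figures were 30% vs 30%. With all risk in the first 3 months they were 30% vs 31%.

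**5. Accrual order alone.** With the step 3 formula, a median of 8 months in both arms and an assumed follow-up of 22.3 vs 15.4 months, P is 0.349 vs 0.321. In simulations where every patient had at least 12 months' follow-up, a crude 30% in Arm B became 31% to 33% in Arm A.

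**6. Fixed window.** Use the same formula with F set to the window (at 30.44 days per month) and medians of 8 vs 4 months. Eighteen weeks (F = 4.14) gives 15.8% vs 13.5%. Twelve weeks (F = 2.76) gives 11.5% vs 10.3%. The gap of about 10 points falls to about 2 and about 1.

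**7. Events per patient-month.** Under a constant hazard this rate is equal in both arms. Under early toxicity it is not. Assume that all risk falls in the first 6 weeks (1.38 months) and that a patient treated throughout has a 30% risk, so h = −ln(0.7)/1.38 = 0.2585.

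- Median 4: P = 0.2585/0.4318 × (1 − exp(−0.4318 × 1.38)) = 0.269. Mean time on treatment to 15.4 months = (1 − exp(−0.1733 × 15.4))/0.1733 = 5.37 months. Rate = 5.0 per 100 patient-months.
- Median 8: P = 0.2585/0.3451 × (1 − exp(−0.3451 × 1.38)) = 0.284. Mean time = 8.50 months. Rate = 3.3 per 100 patient-months.

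With the same early hazard, the longer-treated arm looks about one third less toxic.

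**The case against.** **The 8 vs 4 contrast may rarely reach the comparison.** Four months is the historical single-agent figure, not a forecast for either arm. The question of similar toxicity arises in Section 8.0 only when both arms have met the criteria, and an arm with a 4-month median gets there only through ORR of at least 50%. This stands, and it is why 3 to 5 points is the fairer size when both arms qualify on PFS. Section 2.1 does compare safety profiles between arms without that condition, so the larger contrast is not ruled out.

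**Toxicity may be early.** If so, the distortion almost vanishes (step 4). The documents give no hazard and no timing profile. They do expect some late events: Section 5.2.1.2 allows for pembrolizumab events months after the last dose, Section 5.6.2 for thyroid disorders throughout treatment, and Section 5.4 for later-cycle toxicity to lower the RP2D.

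**Noise exceeds bias.** With 12 per arm, the standard error of the difference at 32% vs 22% is √(0.32 × 0.68/12 + 0.22 × 0.78/12) = 0.18, or 18 points. The comparison is descriptive and the final choice rests on clinical judgment. This stands and limits the weight of the point. But the bias is systematic, and judgment is better served by a table that does not mix duration with toxicity.

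**Accrual order.** A reader might infer that Arm A will look more toxic because it is accrued first. The documents do not support this as a material effect: with 12 months' follow-up for all, it is about 1 to 3 points. It grows only with a data cut soon after the last patient enters. With assumed follow-up of 2 to 10 months in Arm B and 14 to 22 in Arm A, 30% became 40% to 48%. No section plans such a cut.

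**Conclusion.** The point holds as a conditional weakness in the planned safety summary. Crude percentages over a window tied to progression can make the longer-treated arm look more toxic if the arms differ in PFS and to the extent that toxicity keeps accruing. At an assumed 5% monthly hazard and 15.4 months' follow-up, the artefact is about 10 points for medians of 8 vs 4 months, 3 to 5 points for 8 vs 10 to 12, and close to zero if risk ends within 6 to 12 weeks.

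A reader might go further and conclude that the more effective sequence will be penalised for its efficacy. The documents do not show that. Unequal exposure is foreseeable but not established, the hazard is unknown, and when both arms pass the PFS criterion the effect is less than one patient in 12. Nor should events per patient-month be taken as the neutral alternative, because step 7 shows it erring the other way.

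**What to change.** In Section 8.0, keep the crude table and add a by-arm table of the proportion of patients with related Grade 3 or higher events in a fixed window common to all patients, for example the first 12 or 18 weeks from C1D1. Name this table as the basis for the between-arm toxicity comparison, and report time on treatment by arm beside it. Events per patient-month may be shown as a supplementary descriptive figure, with a note that it favours the longer-treated arm when toxicity is early.

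The cost is one extra table, built from event start and stop dates that Section 7.2.4 already requires; no new visits or patients are needed. The downside is that a fixed window misses late events, which is why the crude table stays. The window reduces the dependence on PFS but does not remove it (step 6).
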